A Pilot Study Testing Benefits of Ursolic Acid (UA) as a Countermeasure To Myopenia and Insulin Resistance in Chronic SCI

3. Objectives

To address the need for an agent that maintains muscle mass and attenuates IR after SCI, we propose a 'first-in-humans with SCI' pilot trial that tests benefits of UA as a countermeasure to sarcopenia and IR.

Aim 1

• To explore effects of UA administration on upper extremity lean mass and peak strength in persons with paraplegia.

Aim 2

• To test effects of UA administration in sedentary individuals with tetraplegia on whole body resting insulin sensitivity, glucose/insulin/inflammatory responses to an oral glucose challenge (OGTT), and whole-body lean mass.

4. Study Endpoints

Primary Outcome Measure(s):

- Change in Muscle Mass Using Dual X-ray Absorptiometry (DXA)

 Time Frame: Baseline, 12 weeks
- 2. Change in Peak Isokinetic Strength
 - a. Time Frame: Baseline, 12 weeks
- Changes in Fasting Insulin Resistance (IR)
 a. Time Frame: Baseline, 12 weeks
- 4. Changes in Glucose Disposal
 a. Time Frame: Baseline, 12 weeks

5. Background

The multi-year COVID-19 pandemic has resulted in a decline of overall physical activity, life-satisfaction, and health within the spinal cord injured (SCI) community.¹ **During the pandemic, people with SCI have experienced health decay to a far greater extent than the general population, primarily due to profound social distancing, fears of social engagement and infection, and restrictions in exercise engagement.² Even without social isolation and exercise restrictions, trauma to the spinal cord is typically associated with physical and metabolic disorders that have wide-ranging effects on almost all body systems.³ Our works,⁴ and the works of other investigators⁵ have reported a level-of-injury dependent myopenia – i.e.,** *clinically relevant muscle wasting* **– which is commonly observed following spinal cord injury (SCI), and ultimately compromises post-SCI function, metabolism, body composition, and health. Adjustments to body composition that accompany SCI-related myopenia include a decline of metabolically active muscle mass accompanying the loss of actively contracting muscle, which reduces whole body caloric expenditure and establishes**

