UA will be sourced as Biotech Nutritions Ursolic Acid Gelatin Free Non-GMO capsules (i.e. form) ; 200mg (4 total capsules, 50mg each) taken twice daily by mouth with food and a non-alcohol-containing drink. UA is a non-Rx nutraceutical obtained without prescription. We will neither claim an FDA 'brand' for the product, nor propose a new or extended indication for its use.

Manufacturer: Biotech Nutritions [name] Ph: [name]

- Aim 1: will couple UA administration at doses that increase muscle mass with strengthening exercise performed in one arm only.
 - Subjects will receive 2 bottles of oral UA every month. Subjects will be asked to take 400 mg or 8 capsules (4 in the morning/200mg and 4 at night/ 200mg) daily for 12-weeks
 - Adherence to the UA intervention will be done once a month by study staff and will entail:
 - collection of used bottle(s)
 - counting remaining capsules, if any
 - calculation of compliance: [(days x 8) capsules remaining
 - and dispensing a new bottle(s).

**Education regarding the importance of compliance to the dosing requirements will be part of the monthly drug accountability.

*** Research Studies Subjects will be offered participation in other PM&R and Miami Project to Cure Paralysis studies for which they may be eligible. The possibility of dual enrollment or partial overlap of participation in more than one study is conceivable. This could result in duplication of required assessments subjects would need to complete. However, to simplify participation, reduce the number of visits to our research lab, and mitigate testing redundancy, we may apply test results completed for one study to another in those cases.

- During this period, one upper limb (only), randomized by selection, will undergo exercise conditioning three times weekly using a strengthening program we have established to increase muscle mass and strength in people with SCI. The other arm will remain untrained as a control receiving the same whole body dose of UA.
- Lean mass will be examined before and after 12 weeks of treatment using dual-ray absorptiometry (DXA) and non-contrast CT scan of both arms, with the area of interest identified from the glenohumeral joint distally to the ulnar styloid.
- Peak isokinetic strength of both arms at 90 degrees of flexion will be tested in elbow flexion and extension on a Biodex dynamometer.
- Maximal inspiratory pressure will be measured with the Pro2 Fit device.

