The co-primary outcomes will be lean mass and peak strength.

- Aim 2 subjects will:
 - Subjects will receive 2 bottles of oral UA every month
 - Subjects will be asked to take 400 mg or 8 capsules (4 in the morning/200mg and 4 at night/ 200mg) daily for 12-weeks.
 - Adherence to the UA intervention will be done once a month by study staff and will entail:
 - collection of used bottle
 - counting remaining capsules, if any
 - calculation of compliance: [(days x 8) capsules remaining]
 - and dispensing a new bottles.

**Education regarding the importance of compliance to the dosing requirements will be part of the monthly drug accountability.

*** Research Studies Subjects will be offered participation in other PM&R and Miami Project to Cure Paralysis studies for which they may be eligible. The possibility of dual enrollment or partial overlap of participation in more than one study is conceivable. This could result in duplication of required assessments subjects would need to complete. However, to simplify participation, reduce the number of visits to our research lab, and mitigate testing redundancy, we may apply test results completed for one study to another in those cases.

- Whole body lean mass will be determined by DXA and CT scan before and after 12 weeks of treatment.
- Before and after the 12-week UA intervention an oral glucose tolerance test (OGTT: 75 g glucose as TrutolTM) will be administrated following an overnight fast.
 - Bloods taken before glucose ingestion will be analyzed for glucose, insulin, and inflammatory biomarkers (TNF-alpha, IL-6, and CRP).
 - Bloods will also be taken at 30-minute intervals for two hours.
- Maximal inspiratory pressure will be measured with the Pro2 Fit device.

Co-primary outcomes will be the fasting IR determined by the HOMA v2 model and the rates of glucose disposal defined by the area under the glucose challenge curve (AUC).

Dual X-ray Absorptiometry (DXA)*

The regional composition for Fat Free Mass (FFM), Fat Mass (FM), % FM, and Lean Mass (LM), in regions of interest including the trunk, arms, android, and gynoid regions will be measured by DXA as described by Gorgey et al., Spinal Cord 2018. Body composition will be measured by whole body scans using a GE

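### Aim 1 asks what UA does to arm lean mass and strength, but both arms receive UA and only exercise is randomised: no contrast on these co-primaries separates UA from time, and section 11 names none

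*Combined protocol and SAP*

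**What the plan says.** Section 3 introduces the study as a "pilot trial that tests benefits of UA as a countermeasure to sarcopenia and IR", and words Aim 1 as "To explore effects of UA administration on upper extremity lean mass and peak strength in persons with paraplegia".

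Section 9 says that Aim 1 "will couple UA administration at doses that increase muscle mass with strengthening exercise performed in one arm only". The training is done "using a strengthening program we have established to increase muscle mass and strength in people with SCI". Of the remaining arm it says: "The other arm will remain untrained as a control receiving the same whole body dose of UA".

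Both arms are measured for both outcomes. On mass: "Lean mass will be examined before and after 12 weeks of treatment using dual-ray absorptiometry (DXA) and non-contrast CT scan of both arms". On strength: "Peak isokinetic strength of both arms at 90 degrees of flexion will be tested in elbow flexion and extension on a Biodex dynamometer". Section 9 then states: "The co-primary outcomes will be lean mass and peak strength". Section 4 defines these endpoints as changes between baseline and 12 weeks and names DXA for mass.

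Section 11 randomises which arm trains. UA is not randomised. The analysis is described only as a Bonferroni-corrected repeated measures design for mass and strength, with alpha 0.05 and a non-parametric or transformation fallback. It does not say whether the Aim 1 test is the time effect, the arm-by-time interaction, or the change in one particular arm.

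**The concern.** The question is about UA, but the only randomised factor is exercise. A repeated measures analysis of two arms at two visits offers several tests, and they answer different questions. The arm-by-time test is a randomised comparison, but a UA effect common to both arms drops out of it. The time effect pooled over arms, and the trained arm's change, include training that the protocol itself says is established to raise both co-primaries, so a gain there is expected even if UA does nothing. The untrained arm's change is free of direct training but has no UA-free comparison.

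Because section 11 leaves the choice open, a significant result from any of these could be reported under a UA aim. Bonferroni controls the number of tests; it does nothing about what each test confounds.

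**Working it through.** The plan gives no sample-size or power figure for Aim 1, so there is none to reproduce. The check is whether a UA effect can be estimated from the planned data.

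**Inputs.** UA in both arms, training in one (section 9); the training arm randomised (section 11); measurement at baseline and 12 weeks (sections 4 and 9); at most 10 participants (section 6). The text available for review contains no UA-free group, run-in or external comparator. Aim 2 cannot supply one: its participants also take UA, and they have a different injury level.

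**Model.** For each co-primary let U be the UA effect common to both arms, T time and retest, E exercise (including any interaction with UA), and C carry-over of training to the untrained arm. Then

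- trained-arm change = T + U + E
- untrained-arm change = T + U + C

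The design matrix for the four cell means is:

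| Cell | Base, trained | Base, untrained | T | U | E | C |
|---|---|---|---|---|---|---|
| Trained, baseline | 1 | 0 | 0 | 0 | 0 | 0 |
| Trained, week 12 | 1 | 0 | 1 | 1 | 1 | 0 |
| Untrained, baseline | 0 | 1 | 0 | 0 | 0 | 0 |
| Untrained, week 12 | 0 | 1 | 1 | 1 | 0 | 1 |

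The rank is 4 with 6 columns, and still 4 with 5 columns when C is set to zero. The T and U columns are identical, so U is not estimable in either case. What can be estimated is E − C, U + T + C and U + T + E; if C = 0, these become E, U + T and their sum.

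**Weights carried by each candidate contrast:**

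| Contrast | T | U | E | C |
|---|---|---|---|---|
| Trained minus untrained | 0 | 0 | 1 | −1 |
| Untrained-arm change | 1 | 1 | 0 | 1 |
| Trained-arm change | 1 | 1 | 1 | 0 |
| Mean change over both arms | 1 | 1 | 0.5 | 0.5 |

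No row has weight on U without the same weight on T. This needs no assumed effect size.

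**Illustration (drift sizes are assumptions).** Suppose UA has no effect, n = 10, and the untrained arm's change is tested two-sided at 0.05/2 = 0.025. By the noncentral t distribution, drift unrelated to UA of 0, 0.25, 0.5 or 0.75 SD of change gives a significant result in 2.5%, 6.2%, 19.2% or 42.2% of trials.

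**Precision of what can be reported.** n = 8 is an assumed number of completers, because enrolment is capped at 10 and participants with low adherence are withdrawn.

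- Untrained-arm change, 95% CI half-width in SD of change, t(0.975, n−1)/√n: 2.262/√10 = 0.72; 2.365/√8 = 0.84.
- Arm difference, 97.5% CI half-width in SD of the within-person difference, t(0.9875, n−1)/√n: 2.685/√10 = 0.85; 2.841/√8 = 1.00.
- Arm difference detectable with 80% power, paired t test, two-sided 0.025, noncentral t: 1.14 SD (n = 10); 1.34 SD (n = 8).

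**The case against.** The strongest reply is that this is an openly exploratory, uncontrolled pilot. Aim 1 says explore, section 4 defines the endpoints as changes from baseline, section 9 couples UA with training, and the language of testing benefits belongs to the trial-level statement rather than to Aim 1. Much of this stands. A single-group pilot is a legitimate choice, and the wording of the aim lowers the severity. It does not settle which change is meant, and section 11 still sets significance testing on named co-primaries.

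A reader might infer that the plan disguises its control arm. The documents do not support that: section 9 says plainly that this arm is untrained and on the same UA dose, and section 11 says that exercise is what is randomised. What is missing is the inferential consequence.

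It can also be argued that drift will be small. Eligibility requires injury of at least one year, and section 5 places obligatory sarcopenia within the first year. That may limit drift in lean mass, so the two co-primaries need not be equally exposed. It does not remove retest effects in strength, does not show that drift is zero, and does not make UA estimable.

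Finally, making the arm difference the tested contrast answers a training question with little power. That is true. It is proposed because it is the only randomised comparison, and it must not be presented as evidence on UA.

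**Conclusion.** The point holds for the two Aim 1 co-primaries. No analysis of the planned data separates UA from time: UA has weight 0 in the arm difference and is inseparable from time in every change from baseline. Section 11 as written would answer a UA aim with a test that either cancels UA or mixes it with time, retest, carry-over or training. The algebra rests only on both arms receiving UA over the same 12 weeks and on there being no UA-free comparison; the precision figures also rest on approximately normal changes and, for n = 8, on the assumed completers.

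This should be fixed, but it does not invalidate the pilot. Three stronger readings are not supported. The untrained arm does not show UA alone. The arm difference is not exercise alone, because it is E − C unless carry-over is zero. And the contrast with Aim 2 is not one of uncontrolled against controlled: all Aim 2 participants also take UA, with no comparator. Aim 2 and the other Aim 1 measures are otherwise outside this point.

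**What to change.** 1. In section 11, name two contrasts for each Aim 1 co-primary.
   - (a) The untrained arm's 12-week change, reported with a 95% CI as an uncontrolled change during UA, with time, retest and possible carry-over included, and not as a UA effect.
   - (b) The within-person trained-minus-untrained difference in change, tested by paired t test (Wilcoxon signed-rank under the existing non-parametric rule) at 0.025 per co-primary. Interpret it as the effect of one-arm training during UA, net of any carry-over to the untrained arm, and not as evidence on UA.

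   The 0.025 level holds with one measure per co-primary: DXA lean mass, as in section 4, and one elbow strength measure that the sponsor names before analysis. Sections 8 and 9 should be read together with this choice, since section 9 lists flexion and extension, and peak and average force.
2. State in section 11 that no pooled time effect, trained-arm change or arm difference will be reported as a UA effect.
3. In section 9, describe the untrained arm as a control for exercise, not for UA.
4. In section 3, qualify Aim 1: to explore the uncontrolled 12-week change in arm lean mass and peak strength during UA, and the effect of one-arm training during UA, net of carry-over. If a caveat is added to the trial-level sentence on benefits, word it to cover both aims.

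**Cost.** Wording in three sections and a narrower Aim 1 claim; no new participants, visits or data. Estimate (a) is imprecise and test (b) can detect only large differences, at the sizes shown in the working. A concurrent UA-free group measured on both arms would make UA estimable, but that is a different and larger study and is not needed for this correction.

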Lunar Prodigy Advance scanner (GE Lunar Inc., Madison, WI,USA). Transfer to the DXA scanner will be performed using either a ceiling lift or assisted self-transfer with or without sliding board. Participants will be instructed to take off any metal, void their bladder, and dress in light clothes prior to transfer to the DXA table. Using the NHANES scanning method, both knees will be bound together using a large Velcro strap. Above the knee joints and each leg is placed in neutral position with the great toe facing upwards. Because of the difficulty in keeping the arms close to the body in large individuals or in cervical SCI, arms will be strapped near the body in the mid-prone position to ensure the total body is within the scanning field. The standard mode scan will be used with a radiation dose of 0.4μ Gy. Scans are performed and analyzed by a certified DXA operator using current Lunar software. As part of quality assurance, the DXA scanner will be calibrated using a quality control phantom (L: 197.7, W: 60.1) according to the manufacturer guidelines for both short-term and long-term precision studies.

Non-contrast CT images (Structure)*

Computed tomography (CT) is a radiographic method that produces thin crosssectional high-resolution images that may better differentiate and measure volumes of fat and lean tissue when compared to DXA. For this pilot study, chest, abdominal and upper extremity/arm scans will be performed at UM/Sylvester Department of Radiology; these will be obtained pre- and post-intervention using a 128-slice multi-dimensional whole-body scanner before and after the intervention. Before the scan, subjects will have their upper extremities ranged. Images for upper extremities will be attained from the glenohumeral joint to the hand. All images will be analyzed at a separate workstation using TeraRecon iNtuition imaging software.

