Images are automatically segmented into adipose tissue, skeletal muscle, and bone/background based on location and their attenuation properties, with adipose having the lowest attenuation and bone/background having the highest attenuation. A CT attenuation range of -120 to -40 Hounsfield units (HU) will be used to encompass abdominopelvic adipose tissue, -190 to -30 HU will be used for intra muscular fat (IMF), and -29 to +150 HU will be used for skeletal muscle (needed for IMF quantification). Cross-sectional area (CSA; cm2) will be automatically calculated by the software by summing the pixels of the tissue and multiplying it by the pixel surface area for each adipose tissue depot, while volume (cm3) computed by multiplying the CSA by the image slice thickness and inter-slice space. Visual distinction will be used to determine visceral adipose tissue (VAT), subcutaneous adipose tissue (SAT), muscle and bone based on the anatomical locations of the tissues and CSA and volumes will be summed together from consecutive slices. Total VAT mass and total SAT mass (in grams) will be the product of the total volume and fat density (0.9196 g/cm₃). To account for muscle size, IMF CSA will be normalized to muscle CSA. The volume of IMF will be calculated as described above. All CT scans will be reviewed by a Radiologist. Subjects will be informed of any incidental abnormalities detected in the CT scans performed for this study and they will be referred to an appropriate provider. In order to do a single scan of the upper limbs and abdominopelvic cavity, the chest will be included in the scan. It will also be reviewed for incidental findings.

*Total effective dose of radiation for DXA and CT scans (total pre and post) is expected to be around 22 mSv (millisievert) or around 7 years worth of background radiation.

Blood Analyte Testing

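### Lean mass is an Aim 1 co-primary, but no DXA or CT reader is masked to time point or trained arm, and the DXA software version is left open

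*Combined protocol and SAP*

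**What the plan says.** **Outcome.** For Aim 1, section 9 states: "The co-primary outcomes will be lean mass and peak strength". Section 11 repeats this pair and plans significance tests with a Bonferroni correction. For Aim 2, both sections name insulin resistance and glucose disposal as co-primaries. Section 4 lists DXA muscle mass as a primary outcome without tying it to an aim.

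**Comparison.** One arm is trained and both arms are exposed to ursolic acid: "The other arm will remain untrained as a control receiving the same whole body dose of UA". Section 11 randomises which arm is trained, by dominance, in equal numbers. Aim 2 is a single group with no randomisation.

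**DXA.** "Scans are performed and analyzed by a certified DXA operator using current Lunar software". Quality assurance covers the machine: "the DXA scanner will be calibrated using a quality control phantom". Section 9 describes the arm scans "with the area of interest identified from the glenohumeral joint distally to the ulnar styloid", without saying who sets that region.

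**CT.** "All images will be analyzed at a separate workstation using TeraRecon iNtuition imaging software". No version is given. The segmentation is largely automatic: "Images are automatically segmented into adipose tissue, skeletal muscle, and bone/background based on location and their attenuation properties", with attenuation ranges fixed in advance. A reader-dependent step is also described: "Visual distinction will be used to determine visceral adipose tissue (VAT), subcutaneous adipose tissue (SAT), muscle and bone", judged by anatomical location.

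**Masking.** The text available for review does not mention masking or blinding of any assessor. Section 12 gives records a numeric ID, as a privacy measure.

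**The concern.** Aim 1 participants know which arm they train, and there is no placebo in either aim. Masked reading is therefore one of the few protections open to the lean-mass measurement. Randomising the arm balances the two arms at the start, but it does not stop a reader who knows the allocation from setting the region slightly differently on the trained side.

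Two separate mechanisms are involved:

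- **Reader bias.** Someone who knows the time point or the trained arm may, without intending to, place a boundary or resolve a tissue edge in the expected direction.
- **Version drift.** If the Lunar software is updated during the 12 weeks, a baseline scan and its follow-up may be analysed by different algorithms.

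With at most 10 participants in Aim 1, a small consistent shift could affect whether the lean-mass test crosses its threshold.

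**Working it through.** The plan gives no effect size, SD, DXA precision error or power, so there is no figure of its own to reproduce. The check has two parts.

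**1. Which bias reaches which comparison**

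Let T be the trained arm and U the untrained arm. DXA is a whole-body scan, and section 9 describes a single CT scan covering the upper limbs, so both arms of a participant come from the same image at each visit.

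- *Additive version shift v at follow-up, equal in both arms.* The contrast is (post_T + v − pre_T) − (post_U + v − pre_U) = (post_T − pre_T) − (post_U − pre_U). The v drops out.
- *The same shift in a pre-post change.* (post + v − pre) = (post − pre) + v. The v stays in full. This applies to either Aim 1 arm alone and to Aim 2 whole-body lean mass.
- *Reader shift r on the trained arm only.* (post_T + r − pre_T) − (post_U − pre_U) = true contrast + r. The r stays in full.

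A reader's shift tied only to time point behaves like v. Only a shift tied to the trained arm biases the between-arm contrast.

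**2. Illustration of size**

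Inputs:
- n = 10 pairs: the Aim 1 ceiling in section 6.
- Two-sided test: assumed; section 11 does not say.
- Level 0.025: assumed, as 0.05 / 2 for two co-primaries. Section 11 states 0.05 and Bonferroni but does not define the family.
- Shift b, in SDs of the tested difference: assumed.

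With no true effect, the paired t statistic follows a noncentral t distribution with n − 1 = 9 degrees of freedom and noncentrality b√n. The false-positive rate is P(|t| > c), where c = 2.685 at level 0.025 and c = 2.262 at level 0.05.

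| Shift b | Noncentrality b√10 | Rate at 0.025 | Rate at 0.05 |
|---|---|---|---|
| 0 | 0 | 2.5% | 5.0% |
| 0.1 | 0.316 | 3.1% | 5.9% |
| 0.3 | 0.949 | 7.9% | 13.6% |
| 0.5 | 1.581 | 19.2% | 29.3% |

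At 0.1 SD the effect is negligible; at 0.5 SD it is serious. Nothing in the documents says where in this range the trial would fall.

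**The case against.** The strongest reply is that the plan already limits reader discretion. The region has anatomical limits, the DXA operator is certified, the scanner is calibrated by phantom, CT segmentation is mainly automatic with fixed ranges, the control is within person, and the trained arm is randomised. All of this stands, and it makes a large shift less likely. None of it hides the time point or the trained arm from the reader. Phantom calibration checks the scanner, not region placement or the analysis version.

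A second reply is that this is a small pilot whose first aim is exploratory. That lowers the stakes, but section 11 still tests lean mass for significance as a co-primary.

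A reader might also infer more than the documents support:

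- *That readers are known to be unmasked.* The documents are silent. The DXA operator is described as a role, with no statement of what that person knows, and some pages, including part of the staff list, were not available for review. The gap is that nothing in the available text requires masking.
- *That both modalities float with the latest software.* The open-ended version wording covers DXA only. For CT, a product is named without a version.
- *That a software change would bias the Aim 1 arm contrast.* An additive shift common to both arms cancels, as shown above.
- *That coding the files would cure everything.* Coding does nothing about version drift. The analyst may also remember a scan or recognise the trained arm from visible hypertrophy.
- *That an Aim 2 co-primary is exposed.* Sections 9 and 11 do not make lean mass a co-primary for Aim 2. Section 4 is ambiguous on this.

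**Conclusion.** The concern holds in a limited form. The available text provides no masking of DXA or CT readers, the DXA version is not fixed, and lean mass is an Aim 1 co-primary. Reader bias linked to the trained arm is the threat to the Aim 1 contrast; version drift is a threat to pre-post changes, including Aim 2 whole-body lean mass.

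The rates of 3.1% to 19.2%, against a nominal 2.5%, illustrate sensitivity and do not estimate what would happen here. They rest on assumed shift sizes, an assumed 0.025 level, a two-sided test and 10 complete pairs. The recommendation does not depend on where in that range the truth lies, because masked batch reading on a fixed version is a better procedure than the one stated and costs little. This should be changed, but it does not undermine the design.

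**What to change.** Add two separate provisions to section 9.

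1. **Masked reading.** After the last visit, existing staff re-analyse all stored DXA and CT scans in one batch and in random order, with participant, date and trained-arm labels removed. The allocation list is withheld from the analyst until the lean-mass results are locked. Where staffing allows, the analyst should be someone who did not perform the scans, since that reduces recall.
2. **Version control.** One fixed software version per modality is recorded and used for both scans of each participant.

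The write-up should say that masking reduces reader bias and may not eliminate it, because hypertrophy or recall can reveal the arm.

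The cost is file coding and one batch session, with final lean-mass values available only after the last scan. No extra scan, visit or radiation is needed. Because stored images are re-analysed, the change can still be made after enrolment has begun.
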